Enrolling people in the study is a three step process. Step 1, is technically a pre-screen, we only want to upload people into DatStat who we think are eligible. If for whatever reason we find out that they are not eligible then we don't want them in the database. You can email [name] and she will delete their entry from DatStat. It is also a good idea for all RAs to keep a list of participants that have been deleted to ensure that you don't accidentally contact them again. Step 2 is the formal screening. If during the formal screening it turns out that they are not eligible then DatStat marks them as ineligible, and they will be removed from your workflow. They do not need to be formally exited from the study. Step 3 is when they sign the consent form during the baseline survey. Once they sign the consent form then, they are officially enrolled in the study. Moving forward, if for whatever reason the person withdraws consent, dies or meets a main study outcome that would be when you officially exit them from the study using the exit survey. The rule of thumb is we only exit people from the study who are officially enrolled, and people are only officially enrolled once they sign the consent form.

Updating or changing participant information once enrolled in study

When updating or changing participant information in Discovery, you can update participant information however you like, including assigning someone to the most accurate study group, prior to the participant signing the consent form. Once a participant signs a consent form, at that time we will consider all the information entered in Discovery to be updated and accurate. At this point some very critical variables such as study arm, race, age, gender, site, language, DOB, can never be changed, even if they are wrong. If at any time after the participant signs a

consent, you realize there is an error in one of these data categories you cannot change the information in Discovery but rather you need you to record that information in a participant log (a word document that you will keep on your computer) and you need to alert [name] of the change. Every few months [name] will ask for a copy of these participant logs. The participant log should include the Participant ID number, the person who made the change in the DatStat system, the original incorrect value and the new corrected value.

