The primary analyses for comparative effectiveness will be based on two-sample independent tests such as t-test, Wilcoxon rank sum test, Fisher's exact test or chi-square test of the outcome measures. The choice of analytic method will depend on whether the outcome measures are continuous or categorical. These tests will be performed at a two-tailed significance level of 0.05 without adjustment for multiplicity. Health care utilization and nursing home placement rates and self-rated health, wellness, depression, and anxiety between the two groups will be compared using a two-sample test again at a two-tailed significance level 0.05.

Subsequent to the primary analyses, regression analyses will be performed for the same outcome measures adjusting for stratification factors and other potential confounders that might influence the outcomes, including an indicator for site. Linear or generalized linear models such as logistic and Poisson regression models will be used depending on the outcome measures. As the intermediary measures of health and overall wellness such as self-rated health, depression, and anxiety in Aim 2 may serve as important mediators of the effect of the peer-to-peer support intervention on the primary outcomes measures in Aim 1, we will use exploratory mixed-effects regression techniques and structural equation models to test and quantify whether and to what extent the effect of the intervention is mediated by intermediary measures of health and overall wellness. We expect missing data due to random drop-out of participants before month 12 and to a lesser extent loss due to death of participants before month 12. Missing data will be handled as per the recent National Research Council report on the topic.⁷⁷ Death before month 12 will be considered a competing event, and will be handled using the appropriate method.⁷⁸

Given the diverse nature of our sample, we plan to carry out the statistical analyses for Aims 1 and 2 for a limited number of subgroups. We will conduct subgroup analyses based on race/ethnicity (African American, Hispanic and non-Hispanic White), gender (male vs. female), age group (< 70, 70-80 and ≥ 80 years), and language (English- vs. Spanish-speaking) and by the three sites. These subgroup analyses will be conducted to evaluate the internal consistency of intervention effect, and subgroup by intervention interaction tests will be used to assess the internal consistency.

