Randomization and matching In order to reduce potential bias further, participants from the AJFCS of Palm Beach will be allocated either to peer-to-peer support (Intervention) or standard community support (Control) in a 1:1 ratio using permuted block randomization, stratified by age, gender and race/ethnicity. Barring randomization in JFS of LA and Community Place of Greater Rochester, older adults already participating in peer-to-peer support and those on the waiting list will be matched on age, gender and race/ethnicity to mitigate potential differences between the two groups. In order to avoid reporting/ascertainment bias, calls will be made to all participating older adults and support staff at 3 and 9 months as outlined in Figure 4 above.

Sample Size Justification Given the total sample size of 720 at-risk older adults, the study has 0.80/0.85/0.90 power to detect the effect size of 0.209/0.223/0.242 for the primary outcome measure of the annualized rate of hospitalization, ED use and institutionalization at a two-tailed significance level 0.05. The effect size here is defined as the difference in the mean annualized rate of hospitalization, ED use and institutionalization between the two groups divided by the standard deviation of the annualized rate assumed to be common in the two groups. Due to random drop-out or loss to competing event of death, the study will have less power to detect the stated effect sizes or will have the stated power for larger effect sizes.

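### The SAP treats death as a competing event but does not link that to the two-sample primary test; equally weighted individual annualised rates lose power, and are biased upward when exit is tied to an event

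*SAP*

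**What the plan says.** **Death.** SAP, Analysis Plan: "Death before month 12 will be considered a competing event, and will be handled using the appropriate method". A reference is cited, but no method, estimand or target outcome is named. Missing data are likewise referred to an external report.

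**Primary analysis.** Same section: "The primary analyses for comparative effectiveness will be based on two-sample independent tests such as t-test, Wilcoxon rank sum test", with Fisher's exact and chi-square tests also listed. Poisson regression appears only among the later adjusted analyses, and no person-time offset is mentioned.

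**Primary outcome.** SAP, Sample Size Justification: "primary outcome measure of the annualized rate of hospitalization, ED use and institutionalization". The definition of the effect size reads: "difference in the mean annualized rate of hospitalization, ED use and institutionalization between the two groups divided by the standard deviation of the annualized rate". No rule is given for the denominator when follow-up is incomplete. The section concedes lower power from drop-out and death but gives no figure.

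**End of follow-up.** Protocol, Enrollment in Study: a participant who withdraws consent, "dies or meets a main study outcome that would be when you officially exit them from the study". Under Exiting the Study, a move to a higher level of care is an exit reason coded as censored, although institutionalisation is a component of the primary rate.

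**The concern.** As written, the death provision and the primary test do not meet. An analyst following the SAP could not tell whether a participant who dies is dropped, annualised over the time observed, ranked, or handled by a separate analysis. These choices answer different questions.

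The natural reading of the effect-size definition is events divided by own follow-up time, averaged over people with equal weight. A person with one admission and one month of follow-up then scores 1/(1/12) = 12 per year. A placement that is counted and also ends follow-up at time t years contributes at least 1/t, which is above 1 for any exit before 12 months. Such scores widen the SD. Where the event and the exit are linked, they also raise the mean. At stake are the power of the primary comparison and whether the estimate reflects utilisation or the timing of deaths and placements.

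**Working it through.** **The SAP's own figure.** With 360 per arm and two-sided 0.05, power = Φ(d·√(360/2) − 1.96). For d = 0.209, 0.223 and 0.242 this gives 0.801, 0.849 and 0.901, so the stated 0.80/0.85/0.90 reproduce. They allow nothing for early exit. Losing 10% of participants alone gives 0.758 at d = 0.209.

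**Assumed inputs (none are in the documents).** Mean 1 event per year with gamma frailty of variance 1; early exit times t uniform between 1/12 and 1 year; where stated, a terminal admission count averaging one (Poisson) per death. Then:
- E[1/t] = ln 12 ÷ (11/12) = 2.711
- E[1/t²] = 11 ÷ (11/12) = 12
- E[t] = 13/24 = 0.542

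**Case A: exit unrelated to events.** The mean individual rate stays at 1. Its variance given t is 1 + 1/t, so with a proportion p leaving early the variance is 2 + 1.711p. At p = 10% it is 2.171 (9% above 2). At p = 30% it is 2.513 (26% above). The cost is precision only.

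**Case B: death with a terminal admission, in a proportion q, no drop-out.**
- Mean individual rate = 1 + 2.711q, which is 1.136 at 5% and 1.271 at 10%.
- Pooled events per person-year = 1 + q/(1 − q + 0.542q), which is 1.051 and 1.105.
- The mean square is 2 + 3(2.711) + 2(12) = 34.13 in those who die and 3 in the rest.
- SD at 5% = √(0.95·3 + 0.05·34.13 − 1.136²) = 1.81. At 10% it is √(0.90·3 + 0.10·34.13 − 1.271²) = 2.12. With full follow-up it is √2 = 1.41.
- At 10% deaths, those who die supply 0.10 × 3.711 ÷ 1.271 = 29% of the summed rate.

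**Power by simulation.** Rate ratio 0.7, 360 per arm, 12 months, 10% drop-out:

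| Scenario | t-test | Wilcoxon | Events per person-time, robust variance |
|---|---|---|---|
| 5% deaths, no terminal admission | 0.85 | 0.79 | 0.88 |
| 5% deaths, one terminal admission on average | 0.65 | 0.75 | 0.86 |
| 10% deaths, one terminal admission on average | 0.53 | 0.70 | 0.83 |

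**A second assumed model.** Drop-out hazard 0.10/year, death hazard 0.05/year and linked to frailty, 70% of deaths preceded by a hospital event, minimum follow-up one day.
- At 12 months the mean individual rate is 1.23 against 1.01 pooled. Adding placement at 0.05/year as an event that ends follow-up gives 1.56 against 1.06.
- At 6 months, the horizon of the pooled three-site comparison, the pairs are 1.22 against 1.02 and 1.53 against 1.07. The upward shift is therefore not confined to 12 months.
- At 12 months, t-test power is 0.42 and 0.19, against 0.86 and 0.85 for person-time. These are extreme values, because follow-up as short as one day is allowed.

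**Type I error in the second model, without placement.** With equal true rates and equal deaths the t-test rejected in 2.9% of runs. With the death hazard doubled in one arm it rejected in 7.5%, against 4.3% for person-time.

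**The case against.** **The plan could handle death.** A reader might infer that a two-sample analysis cannot accommodate a competing event. The documents do not support that. The list of tests is introduced as examples, two-sample tests for competing risks exist, a rank test can include death under a stated ranking rule, and a method is promised by citation. What stands is that none is specified or tied to the primary test.

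**Early exit does not inflate rates in general.** The SAP expects mainly random drop-out, with death a smaller cause. Under that expectation the mean is unbiased, as Case A shows. The Protocol also leaves the main study outcome undefined in its exit rule, and hospitalisation and ED use are not among its exit reasons. Upward bias needs exit tied to an event.

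**The SAP's power statement is not contradicted.** One could fix a raw difference of 0.209 × 1.414 = 0.296, let the SD grow to 1.81 or 2.12, and report power of about 0.59 or 0.47. That is power at standardised effects of about 0.164 and 0.14. The SAP standardises by the SD of the rate itself and states no raw difference, so this is not power at its 0.209.

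**The loss depends on the test and on capture of events.** The SAP also names Wilcoxon, which loses much less. Events come largely from self-report, with the first call due around 3 months. Chart requests go only to hospitals the participant reported, and after a death a new signature is needed. Calls to support staff may recover some events, but full capture of terminal admissions from month 1 is an assumption. The t-test loss is smaller if early deaths contribute no recorded event, or if each death carries exactly one admission rather than one on average.

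**The individual-rate reading is inferred.** It follows from the mean-and-SD definition, but no formula is given.

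**Conclusion.** The point holds in a limited form. The competing-event provision is unnamed and unconnected to the primary two-sample test, and the effect-size definition points to equally weighted individual rates with no rule for short follow-up. When exit is unrelated to events the cost is modest: 0.85 for the t-test against 0.88 for person-time. When deaths carry a terminal admission, t-test power is about 0.65-0.53 and Wilcoxon 0.75-0.70, against 0.86-0.83 for events per person-time, and the mean individual rate exceeds the pooled rate (1.27 against about 1.10 at 10% deaths).

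All event, death and drop-out rates are assumptions, and the power figures in the table are for 12 months only. The harm shown is mainly lost power and a distorted estimate. No type I error inflation appeared with equal deaths, and a modest excess appeared when deaths differed between arms. This is a change that should be made to the SAP; it does not show that the trial cannot answer its question.

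**What to change.** - Make the primary comparison of the utilisation rate a rate ratio of total events per person-time: negative binomial or Poisson regression with a log person-time offset and robust standard errors, including every enrolled participant.
- Run person-time to the last date through which events were ascertained. Running it to death while events are known only to the last contact would undercount events in those who die.
- Analyse institutionalisation by cumulative incidence with death as the competing event, and reconcile its place in the primary rate with the Protocol's coding of the same move as censored.
- Add a sensitivity analysis that counts death as an event, so that fewer admissions through earlier death are not read as benefit.
- Name the method for death, and state the denominator rule for both the 6-month and 12-month comparisons.

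**Cost.** SAP wording and slightly more analysis. Exit dates and reasons are already recorded and contact attempts are logged, which helps to fix the ascertainment date. They do not recover events between the last contact and death, so some of these may be missed, and the report should say so.

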The Effectiveness of Peer-to-Peer Community Support to Promote Aging in Place

Principal Investigator: [name]

Protocol Version Date: 10/30/2017

Coordinating Center: University of Wisconsin

Co-Investigators

[name]-University of Wisconsin
[name]- Alliance for Children and Families
[name]- Alpert Jewish Family and Children's Service
[name]- Community Place
[name]- Jewish Family Service of Los Angeles

Study Coordinator: [name]

Funding Sponsor: Patient Centered Outcomes Research Network (PCORI)

Statistical Considerations

In this section, we outline in detail the strengths of our proposed sampling and analysis plan and how it is designed to address and minimize the potential limitations of our study design. Specifically, we elaborate on how we plan to make our samples in the peer-support and standard community services group comparable, despite the fact we cannot randomize all participants; how we will control for differences across sites in our analyses; and how we will deal with missing data (including loss to follow-up).

Analysis Plan The mixed experimental and quasi-experimental, matched group comparison design allows us to conduct three different analyses to accomplish both Aims 1 and 2: (1) comparing the effectiveness of peer support to standard community services at 6 months combining data from all three sites; (2) analyzing the data from AJFCS and the combined data from the other two sites to assess the internal consistency of the effectiveness across the randomized and non-randomized designs but also to assess whether the effect size is different between the two components of the study design; (3) analyzing data from AJFCS to test whether peer-support is more effective when provided for 12 months compared to 6 months. For the third analysis using AJFCS data only, we will compare 12 vs. 6 month "dose"-levels of the peer-to-peer support intervention changes in the rates of health care utilization and nursing home placement and self-rated health, wellness, depression, and anxiety of between baseline and 12 months in group randomized to get peer support relative to changes in these same measures between 6 and 12 months in the group randomized to standard community services; as reminder this group received standard services for 6 months and then transitioned into receiving peer-support between 6 and 12 months (see Figure 3).

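### A non-significant interaction test cannot show that effects agree across sites or designs, and analysis (2) states no method or criterion for judging agreement

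*SAP*

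**What the plan says.** The SAP's Analysis Plan pools all three sites in analysis (1). Analysis (2) takes AJFCS separately from the other two sites in order to "assess the internal consistency of the effectiveness across the randomized and non-randomized designs", and also to see whether the effect size differs between them. No test, interval, margin or decision rule is given for analysis (2).

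The same section lists subgroup analyses by race/ethnicity, gender, age group, language and site, and says that "subgroup by intervention interaction tests will be used to assess the internal consistency". No margin is given there either. On error rates for the primary tests it says: "These tests will be performed at a two-tailed significance level of 0.05 without adjustment for multiplicity".

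Under Randomization and matching, AJFCS participants are allocated "in a 1:1 ratio using permuted block randomization, stratified by age, gender and race/ethnicity". At the other two sites, current recipients of peer support are matched to people on the waiting list. On the SAP's account, then, AJFCS is the only randomised site.

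The only power statement is in Sample Size Justification. It assumes 720 participants in all and concerns the pooled comparison: "the study has 0.80/0.85/0.90 power to detect the effect size of 0.209/0.223/0.242 for the primary outcome measure".

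**The concern.** The null hypothesis of an interaction test is that the effects are equal. Failing to reject it shows agreement only if the data could have revealed a difference that matters. The SAP names this test as its tool for consistency across subgroups and sites, and gives analysis (2) the same aim with no tool at all. Because design is fixed by site, the site-by-intervention test is also the only stated route to the comparison of designs.

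The pooled estimate mixes a part described as randomised with a part that compares current recipients with people on a waiting list. If selection produces some or all of the apparent effect in the second part, the comparison between parts is where it should show. If that comparison is imprecise and non-significance is read as consistency, the pooled result can gain support that the data do not give it.

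**Working it through.** **Inputs.** From the SAP, Sample Size Justification: N = 720, two-sided alpha 0.05, and effects in SD units, that is, a difference in means "divided by the standard deviation of the annualized rate assumed to be common in the two groups". From the Protocol's Recruitment Goal paragraphs: AJFCS 300 (150 + 150), Community Place 226 (113 + 113), JFS of LA 60 (30 + 30). The non-randomised part is therefore 226 + 60 = 286, and the total is 586. The SAP does not split the 720 by site, so several splits are tried. Equal arms, no dropout and no covariate adjustment are assumed.

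**1. The plan's own figure.** The SE of the pooled effect is sqrt(4/720) = 0.0745. For 0.209, power = Φ(0.209/0.0745 − 1.96) = 0.80. Effects of 0.223 and 0.242 give 0.85 and 0.90. The stated figures reproduce.

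**2. Precision of the difference between parts.** SE = sqrt(4/nA + 4/nB). For 300 and 286 this is sqrt(0.01333 + 0.01399) = 0.165, and the 95% half-width is 1.96 × 0.165 = 0.324. The 80% detectable difference is 2.80 × SE.

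| AJFCS / other sites | SE | 95% half-width (SD) | Power at 0.209 | Missed | 80% detectable (SD) |
|---|---|---|---|---|---|
| 300 / 286 (Protocol goals) | 0.165 | 0.324 | 0.24 | 76% | 0.46 |
| 360 / 360 | 0.149 | 0.292 | 0.29 | 71% | 0.42 |
| 300 / 420 | 0.151 | 0.296 | 0.28 | 72% | 0.42 |
| 240 / 480 | 0.158 | 0.310 | 0.26 | 74% | 0.44 |

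Splitting 720 in the Protocol's proportion (about 369 / 351) gives the same half-width and power as 360 / 360. Every half-width exceeds 0.209, so even identical observed effects would leave a difference as large as the planned effect inside the interval.

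**3. The test by three sites.** With 300, 226 and 60, and both non-randomised sites shifted by 0.209 SD, the 2-df interaction test has power 0.19. For a two-level subgroup factor whose smaller level holds 20% or 10% of 720, power at 0.209 SD is 0.20 or 0.13.

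**4. How often the harmful pattern arises.** Suppose the true effect is zero at AJFCS and the other sites show only a selection bias b. The pattern of interest is a significant pooled result with a non-significant interaction. From 1,000,000 simulated draws per case:

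| b (SD) | 360 / 360 | 300 / 420 | 300 / 286 |
|---|---|---|---|
| 0.209 | 0.21 | 0.27 | 0.18 |
| 0.30 | 0.25 | 0.32 | 0.24 |
| 0.418 | 0.16 | 0.19 | 0.20 |

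Given a significant pooled result, the interaction misses the bias in 71% to 75% of cases at b = 0.209, 48% to 56% at 0.30 and 20% to 29% at 0.418.

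**5. Could agreement be shown formally?** The documents give no margin. If 0.209 SD were taken as one, two one-sided 5% tests need a 90% interval inside it. That interval's half-width is 1.645 × 0.149 = 0.245 at best, so agreement could not be shown at 720 even if the parts agreed exactly. About 3,137 participants would be needed for 80% power. With an assumed margin of 0.30 SD the chance is 0.20 to 0.29 at 720 and 0.14 at 586.

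**The case against.** Several stronger readings are tempting, and the documents do not support them.

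- A reader might infer that the SAP judges the two designs by an interaction test. The sentence on interaction tests governs the subgroup analyses and reaches the design contrast only because site is one of the subgroups. Analysis (2) names no test and expressly asks whether the effects differ. The fair criticism there is that method and criterion are missing.
- A reader might infer that the pooled result will look corroborated when it is only selection. No passage says that non-significance will be reported as consistency. Corroboration also needs a significant pooled result, and the full pattern occurs in about 16% to 32% of the cases computed. That supports can, not will. The 71% to 76% is the miss rate of the test, not the probability of this harm.
- A reader might infer that the pooled sample is mostly non-randomised. By the Protocol's goals it is 286 of 586, or 49%.
- A reader might infer that consistency is the SAP's main defence against bias. It also relies on randomisation at AJFCS, matching elsewhere, and regression adjusted for confounders and site. These are real protections, but matching and adjustment address measured factors only, and a site indicator does not remove selection within a site.

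It is also fair to say that separate AJFCS results are already planned, so a reader would see them. They are imprecise, however: with 300 participants, power at 0.209 SD is 0.44. Finally, these are secondary analyses, and the primary test is unaffected.

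**Conclusion.** The point stands in limited form. The SAP's stated tool for consistency cannot show agreement, and analysis (2) has no stated tool. The 95% interval for the difference between parts extends about 0.29 to 0.32 SD either side, against a planned effect of 0.209 SD, and a true difference of that size is missed about 71% to 76% of the time. Selection at the non-randomised sites can therefore go unnoticed.

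The figures assume a common SD, equal arms and full follow-up. The SAP concedes that "Due to random drop-out or loss to competing event of death, the study will have less power to detect the stated effect sizes" but gives no rate; losses would widen the intervals. The use of 0.209 SD as a yardstick is this review's choice: it is the pooled detectable effect, not an agreement margin set by the documents.

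Two limits would remain even with a precise test. With a single randomised site, a difference between parts cannot be assigned to design rather than to site. The Protocol also describes AJFCS differently from the SAP: its AJFCS recruitment section sets current recipients against controls recruited from the community, and its Matching section includes AJFCS. If that is how the groups were formed, agreement between parts would not exclude selection shared by both.

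**What to change.** In the SAP's Analysis Plan:

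1. For analysis (2), report the AJFCS effect, the Community Place plus JFS of LA effect and the pooled effect side by side on one scale, and the difference between the two parts with a 95% confidence interval. Present the subgroup analyses in the same way, as estimates with intervals for the differences.
2. State that a non-significant interaction will not be reported as consistency, and that at this sample size agreement to within the planned effect cannot be established.
3. Describe any difference between the parts as reflecting site and design together.
4. Before AJFCS is presented as the randomised reference, reconcile the Protocol's AJFCS recruitment and Matching sections with the SAP's Randomization and matching section.

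A formal equivalence margin is optional. If one is used, it should be set and justified in advance.

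The cost is SAP wording, one table and a weaker consistency claim. No new data are needed, and the primary test does not change.
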